7.20 Data Collection

All data outlined in schedule of events and in sections below will be collected on case report forms.

Screening data will be collected on screen-fails. Patients who complete the informed consent process and do **not** meet all entry criteria and therefore who do not receive everolimus or placebo will be considered screen failures. Screen failures should be documented as ineligible in the database.

All study data will be collected via systems created in collaboration with the RDCRN Data Management and Coordinating Center and will comply with all applicable guidelines regarding patient confidentiality and data integrity.

7.21 Inclusion/Exclusion Criteria

Information regarding eligibility criteria will be entered on the Inclusion/Exclusion CRF, for both the double-blind and open-label phases. Patients who do not meet all entry criteria for a given phase of the study should not be entered into that phase.

7.22 Patient Demographics/Clinical Interview (Medical History)

Data will be collected on patient characteristics including demographic information (age, sex, race, weight) and other background or relevant medical history (disease history, family history of disease, psychiatric history, prior therapies, hepatitis and HIV history), and any other assessments that are done for the purpose of determining eligibility for inclusion in the study. For women of childbearing potential, serum pregnancy test will be required at screening for eligibility and again at the end of the study. Urine pregnancy test may be used for onsite visits (if deemed clinically necessary).

Physical examination must include a total body examination (general appearance, skin, neck, including thyroid, eyes, ears, nose, throat, lungs, heart, abdomen, back, lymph nodes, extremities and a basic nervous system neurological exam). Physical examinations will occur at the screening and month 6 (visit 8). A physician will evaluate patient at each visit for significant changes and AEs per parent report. If noted, the physician will initiate a PRN physical exam as detailed above.

^{**} Fasting glucose will constitute 2.0 mL of this amount and be collected in a separate tube.

^{***}Additional everolimus levels may be drawn if a dose adjustment occurs due to toxicity or due to concomitant medication dose adjustment.

[#] Visits may occur in person or by phone, no blood collected.

[^] Procedures completed at the Double-Blind Month 6 visit will qualify as Open-Label baseline procedures, as applicable.

[‡] Visits occur in both Double-Blind and Open-Label treatment phases, as applicable.

[×] Optional blood samples can be collected at either the screening or baseline visit

Significant findings made after the start of study drug that meet the definition of an Adverse Event must be recorded.

7.23 GCP Statement

This clinical trial will be conducted in accordance with the ethical principles that have their origin in the Declaration of Helsinki, and that are consistent with Good Clinical Practice and all applicable regulatory requirements.

8. Benefits

Treatment on this study may or may not improve the cognitive and behavioral symptoms of individuals with PTEN gene mutation. Information learned from this study may help patients with PTEN that are impacted by behavioral and cognitive dysfunctions by better describing the neurocognitive deficits and the safety and efficacy of available treatments.

9. Risks

Study Drug: This research study may involve unpredictable risks. Problems or side effects that are not now known could also occur. The participant will be given any new information that may affect their willingness to start or continue themselves or their child in the study.

One of the most common possible side effects of the study drug, everolimus, are mouth lining changes (stomatitis) manifested as redness, irritation, swelling in the mouth or mouth ulcers (Section 6.3).

Sample collection: there is a minor risk of pain, bleeding, bruising, or infection. Any additional biological specimens to be used in future genetic and molecular studies will be obtained from skin or left-over tissue obtained from a clinically-indicated procedure. Such procedures could include the minor risk of pain, bleeding, bruising, or infection

Loss of Confidentiality: minor risk for a loss of confidentiality. Strict patient confidentiality will be observed throughout all aspects of the study. While medical records will be reviewed by members of the research team, no individually identifiable patient data will be distributed to non-research or care-giving team members. All data collected as a part of this study, with the exception of photos/videos, will be de-identified prior to being uploaded into our consortium database, or sent to another site.

10. Study Records Retention

Data will be stored for at least two years following study completion.

11. Sample Destruction

All specimens and the derivatives from them will be stored indefinitely unless the participant withdraws from the study and requests the destruction of samples in writing.

12. Protocol Deviations

Any deviations from the protocol will be logged at each individual site and reported to the central IRB (or local IRB for non-reliant sites) at time of continuing review. This information will also be captured on the protocol deviation CRF in the database. Any significant deviations will be reported within 24 hours to the central IRB.

13. Adverse Event Criteria and Reporting Procedures

Information about all adverse events, whether volunteered by the subject, discovered by investigator questioning, or detected through physical examination, laboratory test or other means, will be collected and recorded and followed as appropriate.

13.1 Definitions and Reporting

An adverse event is defined as the appearance of (or worsening of any pre-existing) undesirable sign(s), symptom(s), or medical condition(s) that occur after patient's signed informed consent has been obtained. Abnormal laboratory values or test results occurring after informed consent constitute adverse events only if they induce clinical signs or symptoms, are considered clinically significant, require therapy (e.g., hematologic abnormality that requires transfusion or hematological stem cell support), or require changes in study medication(s).

Conditions, or symptoms, that are present at the time of informed consent should be recorded on the Medical History CRF and be entered into the database. Adverse events that occur after informed consent should be recorded on the running AE log, as well as on the Adverse Events CRF and be entered into the database Adverse event monitoring should be continued for at least 28 days (or 5 half-lives, whichever is longer) following the last dose of study treatment. Adverse events (including lab abnormalities that constitute AEs) should be described using a diagnosis whenever possible, rather than individual underlying signs and symptoms. When a clear diagnosis cannot be identified, each sign or symptom should be reported as a separate Adverse Event.

Adverse events will be assessed according to the Common Terminology Criteria for Adverse Events (CTCAE) version 4. If CTCAE grading does not exist for an adverse event, the severity of mild, moderate, severe, and life-threatening, corresponding to Grades 1 - 4, will be used.

The occurrence of adverse events should be sought by non-directive questioning of the patient at each visit during the study. Adverse events also may be detected when they are volunteered by the patient during or between visits or through physical examination, laboratory test, or other assessments. As far as possible, each adverse event should be evaluated to determine:

- 1. The severity grade (CTCAE Grade 1-4)
- 2. Its duration (Start and end dates or if continuing at the Safety Follow-up Visit)
- 3. Its relationship to the study treatment (Reasonable possibility that AE is related: No, Yes)
- 4. Action taken with respect to study or investigational treatment (none, dose adjusted, temporarily interrupted, permanently discontinued, hospitalized, unknown, not applicable)
- 5. Whether medication or therapy was given (no concomitant medication/non-drug therapy, concomitant medication/non-drug therapy)
- 6. Outcome (not recovered/not resolved, recovered/resolved, recovering/resolving, recovered/resolved with sequela, fatal, unknown)
- 7. Whether it is serious, where a serious adverse event (SAE) is defined as in 13.3.1.

All adverse events should be treated appropriately. Such treatment may include changes in study drug treatment including possible interruption or discontinuation, starting or stopping concomitant treatments, changes in the frequency or nature of assessments, hospitalization, or any other medically required intervention. Once an adverse event is detected, it should be followed until its resolution, and assessment should be made at each visit (or more frequently, if necessary) of any changes in severity, the suspected relationship to the study drug, the interventions required to treat it, and the outcome.

Information about common side effects already known about the investigational drug can be found in the Investigators' Brochure (Appendix 1). This information should be included in the patient informed consent and should be discussed with the patient during the study as needed. Adverse event monitoring should be continued for at least 30 days following the last dose of study treatment.

13.2 Laboratory Test Abnormalities

Laboratory abnormalities that constitute an Adverse event in their own right (are considered clinically significant, induce clinical signs or symptoms, require concomitant therapy or require changes in study treatment), should be recorded on the Adverse Events CRF. Whenever possible, a diagnosis, rather than a symptom should be provided (e.g. anemia instead of low hemoglobin). Laboratory abnormalities that meet the criteria for Adverse Events should be followed until they have returned to normal or an adequate explanation of the abnormality is found. When an abnormal laboratory or test result corresponds to a sign/symptom of an already reported adverse event, it is not necessary to separately record the lab/test result as an additional event.

Laboratory abnormalities, that do not meet the definition of an adverse event, should not be reported as adverse events. A Grade 3 or 4 event (severe) as per CTCAE does not automatically indicate a SAE unless it meets the definition of serious as defined below and/or as per investigator's discretion. A dose hold or medication for the lab abnormality may be required by the protocol and is still, by definition, an adverse event.

In the event of a laboratory abnormality that the investigator believes to be inaccurate, repeat testing may be done at a facility geographically close to the participant and then shared with the study team.

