2.1 Primary objective

To evaluate the safety of everolimus compared with placebo in patients with PTEN mutations focusing on NCI CTCAE Grade 3 and 4 adverse events, serious adverse events, and Grade 3 and 4 laboratory toxicities. The primary endpoint will be study drop-out rate due to side effects, comparing everolimus vs. placebo. Based on the published literature and our experience in prior TSC trials we hypothesize that the drop-out rate due to side effects in those receiving everolimus will be similar to those in the placebo group with minimal effect size (< 10% difference). We will also determine the frequency of adverse events by type and severity. We predict that the rate of adverse events will be no more than 10% higher in the everolimus group compared to placebo, but overall severity will be minimal.

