6.3.10 Dosing Modifications In Case of Treatment Related Toxicities

Table 3 Criteria for dose modification/re-initiation in case of toxicity suspected to be related to study treatment

Toxicity	Actions
Pneumonitis	See Table 5
Hyperlipidemia and/or hypertriglyceridemia	Any grade: Treat according to best clinical practice. No specific dose reductions are needed.
Hyperglycemia	Any grade: Treat according to best clinical practice. No specific dose reductions are needed.
Stomatitis	Grade 2: Interrupt study drug until resolution to ≤ grade 1. Restart at same dose. Grade 3: Interrupt study drug until resolution to ≤ grade 1. Reintroduce study drug at the next lower dose level**. Discontinue study drug if stomatitis does not recover to ≤grade 1 within 4 weeks. Grade 4: Discontinue study drug

Other toxicities	Grade 2 and 3: Interrupt administration until resolution to ≤grade 1. Restart at same dose.
	Grade 4: Hold study drug until recovery to ≤ grade 1. Reintroduce study drug at the lower dose level**, if available.
Toxicity requiring interruption for > 6 weeks	Permanently discontinue treatment.
No specific dose adjustments are recommended for Grade 1 toxicity. However, physicians should always	

manage patients according to their medical judgment based on the particular clinical circumstances.

**To determine the next lowest dose level, please refer to Table. 5.

Table 4 Dose modification guidelines for hematologic toxicities

Toxicity	Actions		
Thrombocytopenia Platelet Count	 ≥ 75000/mm³: No change 50000/mm³ to 75000/mm³: Hold study drug until recovery to ≥ 75000/mm³. Reintroduce study drug at the same dose level < 50000/ mm³: Hold study drug until recovery to ≥ 75000/mm³. Reintroduce everolimus at the next lower dose level, if available 		
Absolute Neutrophil Count (ANC)	 ≥ 1000/ mm³: No change 500/mm³ to 1000/ mm³: Hold study drug until recovery to ≥ 1000/mm³. Reintroduce study drug at the same dose level < 500/ mm³: Hold until recovery to ≥ 1000/ mm³. Reintroduce everolimus at the next lower dose level, if available. 		
Febrile Neutropenia	Hold further dosing until ANC ≥ 1250/mm ³ and no fever. Then resume dosing at the next lower dose level** if available.		
Toxicity requiring interruption for >6 weeks	Permanently discontinue treatment.		
Physicians should always manage patients according to their medical judgment based on the particular clinical circumstances.			

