16.4 Laboratory Data Flow

Samples collected as a part of this study will be tracked utilizing the corresponding data collection sheets. These forms will be kept both locally and in the database to ensure that samples are sent to the appropriate laboratories. Samples results will be reported electronically to study sites directly from LabConnect. Additionally, the DMCC will data transfer from LabConnect electronically on a regular basis. All transactions are logged and validated for both methods.

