In objective 1, we will examine the safety and tolerability of everolimus by comparing the 1) dropout rates due to side effects, 2) dropout rates for any reason, and the 3) frequency of specific side effects in those receiving everolimus versus placebo. Based on the published literature and our experience in the tuberous sclerosis trial. we predict that the dropout rates due to side effects will be very similar across everolimus and placebo groups (<10% difference). However, we predict that everolimus will cause higher rates of medication-related side effects (≥10% difference) when compared to placebo. We will use chi-square statistics (or Fisher's exact test depending on cell counts) to compare dropout and rates of specific side effects. Statistical significance will be determined using a one-tailed test Type 1 error rate of α=.05, as only increases with everolimus treatment are expected. No false discovery rate correction will be applied because the concern is maximizing sensitivity to any increase in side effect prevalence with everolimus treatment. For dropout rates, we will also compute Kaplan-Meier survival analyses with discontinuation due to side effects or any reason as separate status endpoints. Number of days from baseline to medication discontinuation will be the time variable. Survival analyses are expected to be under-powered due to the generally low dropout rates expected, but these analyses can be useful for describing temporal trends. To ensure any observed group differences are not influenced by other variables or randomization imbalance, cox and logistic regression analysis will also be conducted with and without conditioning on relevant baseline covariates (e.g., demographics, language and cognitive ability, symptom severity).

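### Grade 3-4 laboratory toxicities are a named focus of the primary objective, but section 17 plans no analysis of them, and the AE data alone would miss those that do not meet the AE definition

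*Combined protocol and SAP*

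**What the plan says.** Section 2.1 describes the primary objective as a safety comparison "focusing on NCI CTCAE Grade 3 and 4 adverse events, serious adverse events, and Grade 3 and 4 laboratory toxicities". The same section sets a different quantity as the endpoint: "The primary endpoint will be study drop-out rate due to side effects, comparing everolimus vs. placebo."

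Section 13.1 says that abnormal laboratory values "constitute adverse events only if they induce clinical signs or symptoms, are considered clinically significant, require therapy", or if they require a change in study medication. CTCAE grade is not on that list. Section 13.2 repeats the rule and adds two statements that pull in different directions: "Laboratory abnormalities, that do not meet the definition of an adverse event, should not be reported as adverse events", but also "A dose hold or medication for the lab abnormality may be required by the protocol and is still, by definition, an adverse event".

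For objective 1, section 17 compares "1) dropout rates due to side effects, 2) dropout rates for any reason, and the 3) frequency of specific side effects". The Kaplan-Meier, Cox and logistic analyses that follow introduce no laboratory outcome. Section 15 describes the monitoring committee's review in terms of AEs and serious AEs.

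The laboratory results themselves are kept. After describing reporting to the sites, section 16.4 says: "Additionally, the DMCC will data transfer from LabConnect electronically on a regular basis."

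**The concern.** The objective lists laboratory toxicities by grade as a separate target. The analysis section never returns to them, so whatever is said about them must come from AE records. Those records are assembled under a rule that does not look at grade and rests partly on whether a physician finds a value clinically significant, a term the protocol does not define.

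What is at stake is whether the trial can report, by arm, how many patients had a Grade 3-4 laboratory value. The analytes most exposed are ones that section 6.3 expects to move on everolimus: it names cholesterol, triglycerides, glucose, hemoglobin and lymphocytes among the most frequent laboratory abnormalities. With 20 patients per arm, one patient is 5 percentage points, and section 17.1 treats a difference of 10% or more on any indicator as meaningful and reportable.

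**Working it through.** **Step 1: which laboratory changes reach the AE data by rule.** Inputs are Tables 3 and 4 (section 6.3.10), section 6.3.8 and the AE definition in 13.1 and 13.2.

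| Laboratory change | Route into the AE data | What can stay out |
|---|---|---|
| Platelets below 75000/mm³, ANC below 1000/mm³ | Table 4 holds drug, and a hold makes it an AE (13.2) | Little |
| Cholesterol, triglycerides | No dose reduction called for at any grade (Table 3). 6.3.8 has Grade 3 values treated as clinically indicated, and therapy makes it an AE | Values left untreated and not judged significant |
| Glucose | No dose reduction called for at any grade; treatment by best practice (Table 3) | As above |
| Other analytes, suspected to be related | Table 3: "Grade 2 and 3: Interrupt administration until resolution to ≤grade 1"; Grade 4 is also held | Little |
| Other analytes, not suspected to be related (e.g. hemoglobin, lymphocytes) | No hold rule; only symptoms, therapy, a drug change or judged significance | Asymptomatic, untreated values not judged significant |

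The exposed group is therefore a Grade 3-4 value that is asymptomatic, untreated, leads to no study-drug change and is not judged clinically significant.

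**Step 2: whether the data for a direct count exist.** Hematology and chemistry are scheduled centrally at screening and Months 1, 3 and 6 (4.3, 7.16.2, 7.16.5), and lipids at screening and Months 3 and 6 (7.16.5). The results go to the coordinating center (16.4). A count by grade needs no new sample.

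**Step 3: the plan's own power figure.** Section 17.1 gives 0.81 for 1/20 against 8/20 at one-sided alpha 0.05. With 20 per arm, power is the sum of Bin(x; 20, 0.05) × Bin(y; 20, 0.40) over all pairs (x, y) for which the one-sided Fisher p-value is at most 0.05. This gives 0.808, so the figure reproduces.

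**Step 4: what incomplete capture would do (illustration only).** The documents give no capture rate. Assume that AE records catch the same share c of events in both arms. The observed rates are then c × 5% and c × 40%, and a true 10-point difference appears as c × 10 points.

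| c (assumed) | Observed rates | Fisher power | True 10 points appears as |
|---|---|---|---|
| 1.00 | 5% vs 40% | 0.81 | 10 |
| 0.90 | 4.5% vs 36% | 0.74 | 9 |
| 0.75 | 3.75% vs 30% | 0.60 | 7.5 |
| 0.50 | 2.5% vs 20% | 0.29 | 5 |

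On average, any c below 1 brings a true 10-point difference under the 10% reporting threshold. Grading the central data directly corresponds to c = 1, which leaves the sample size and the stated power unchanged. The 5% and 40% are the plan's rates for drop-out or side effects in general, not forecasts for laboratory toxicities.

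**The case against.** The strongest reply is that nothing is lost. Section 13.2 governs what goes on the AE form; it does not discard laboratory values or say how laboratory toxicities are to be counted. Section 2.1 lists them apart from AEs, so the objective is not tied to that form, and the numeric results are held centrally. Keeping laboratory values separate from AEs is not in itself an error. Laboratory AEs also fit under the frequency of specific side effects in section 17: section 6.3.1 lists hypercholesterolemia, neutropenia and hypophosphatemia as adverse drug reactions. The analyses are declared to be mainly descriptive. Of the most frequent grade 3/4 reactions in 6.3.1, the only laboratory finding is neutropenia, which Table 4 catches.

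Much of this stands. The hold and therapy routes are real, and platelets and neutrophils are poor examples of a gap. For lipids, it would be wrong to cite the absence of a dose reduction without the direction to treat. Two points survive. First, holding the data is not the same as planning to analyze them, and section 17 names no analysis that uses them. Second, the list in 6.3.1 covers reactions that investigators attributed to treatment, so it does not measure what such judgements leave out.

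A reader might infer that Grade 3-4 laboratory toxicities are undercounted in this trial. The documents do not support that. It would follow only if AE records were the sole source used, and even then the number missed is unknown. Nor is it evidence that two missed patients in 20 would equal the 10-point threshold: that is the arithmetic of a small arm, and it assumes that both misses fall in the same arm.

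**Conclusion.** The point holds as a gap between objective and analysis. One of three named safety targets has no planned analysis, and the records that would otherwise answer for it are filtered by a rule that ignores grade. This is more than missing detail, because a better count is available from data already transferred.

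Its size cannot be derived. The affected values are the narrow group identified in the working, and the power losses shown there rest on assumed capture rates that are equal in both arms. The primary endpoint, drop-out due to side effects, is unaffected. The conclusion rests on reading section 17 as the complete analysis plan; no other section of the protocol plans a tabulation of laboratory results by grade.

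**What to change.** Add a fourth item to objective 1 in section 17, for the double-blind phase:

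- Grade the post-dose central laboratory values by CTCAE from the LabConnect transfer, regardless of AE status.
- Compare by arm the proportion of patients whose worst post-dose grade is 3 or higher. Give the risk difference with an exact interval, the one-sided Fisher test already used in section 17, and apply the 10% reporting rule of 17.1. Since 17.1 says the sample is underpowered for small differences, the estimate and interval should carry the weight.
- Give baseline-to-worst shift tables by analyte. Table 13A puts the pre-dose laboratory sample at screening, so say that this is the baseline.

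Two matters must be settled first. Section 7.13 grades by CTCAE v5.0 and section 13.1 by version 4; these must be reconciled, because the counts depend on the version. Section 13.2 also allows a value believed inaccurate to be repeated at a local facility, so the plan must say which result counts.

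The cost is a little programming and, because section 17 is protocol text, a written amendment with the reviews that section 18 requires. No sample is added, and AE reporting and clinical management stay as they are.
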